Traditional infectious disease models of HCV disease are often based on assumptions about mixing, i.e. that individuals who are infectious and susceptible have contact with all other members of the population. Such models that are not informed by empirically based contact patterns and fail to capture the heterogeneity in individual interactions.^[35] In our study, the ability to collect data on using both blood sampling and social network will allow us to estimate incidence rates in conjunction with estimating the network itself. Our goal is to explore the network role in HCV transmission, including an examination of independent risk factors for transmission. For example how to network size, connectivity or geographic spread impact risk? What are the potential protective network effects? For example, in the rural Appalachian setting, injection drug use network studies revealed that injection of prescription opioids, cocaine, needle sharing, and degree centrality (i.e. connected network position) were associated with increased HCV risk.^[36] Public health and policy intervention that could impact HCV transmission in this case could include prevention of transition to injection among prescription opioid, as well as increased access to opioid maintenance treatment, and syringe exchange. Network position can be useful when employing network-based interventions via dissemination of information, clean needles, and naloxone.

In ETHIC, injection, sexual and social support network data will be collected from participants. Participants will also undergo HIV, HCV and STI screening. Data collected will not be used to attempt to contact network partners (see section “Protection of Third Party Data below). Respondent driven sampling (RDS), a voucher based snowballing type of recruitment will be used. An augmented social network will be generated using matching protocols between participant self-reported networks and RDS connections. Having better connection information than would be obtained through RDS in isolation allows for more variety of network indices to be examined for relevance in interventions. The accuracy of network structure is critical to appropriately inform the universe of available prevention and treatment interventions.

2) Specific aims: The goals of ‘Ending transmission of HIV, HCV, and STDs and overdose in rural communities of people who inject drugs’ (ETHIC) are to:

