Networks among Appalachian People (SNAP) instrument developed by the University of Kentucky, including investigators who are members of the larger UG3 cooperative agreement, Kentucky site.^[12] The survey is attached as Appendix 4. Surveys will be programmed and administered using REDCap and will take approximately 60-90 minutes to complete. Surveys will be performed at the baseline study encounter and then every 6 months until the beginning of the draw down period of the study. Surveys may be performed over videoconferencing, telephone, or through an encrypted link to the REDCap survey.

i) Biosurveys / HIV, HCV, HBV and STD Burden Screening:

Specimen collection and analysis will be based on the standard of care and coordinated with the harm reduction partners and IDPH per existing contracts and provider arrangements. Thus, all aspects of HCV and HIV screening and confirmation that are current standards of care for the harm reduction partners (HRP) will remain unchanged (e.g. obtaining kits, referral to care, results reporting). Screening will be performed at the baseline study encounter and then every 6 months until the beginning of the drawn down period of the study. In the event of state-wide or regional shut down due to COVID-19 CAB specimen collection will be deferred until in-person data collection is possible.

PWUD enrolled for the surveys will be screened at baseline and follow-up to determine disease prevalence and incidence in the population. Participant demographic data, survey responses, and specimen analysis results will be utilized to characterize the disease burden in the rural PWUD population versus the rest of the IDR and national trends and be applied to models of individual factors associated with increased risk.

All participants will provide as part of routine services provided:

- Finger stick sample and/or oral swabs at the time of participation for rapid screening for HIV ,and HCV using commercially-available and FDA-approved rapid assays provided by IDPH.
- Urine specimens for urine toxicology testing using the 10-panel Alere iCup urine toxicology test (point-of-care, with results within 5 minutes) as part of the eligibility screening (see section 4)d. below)
- Urine specimens for FDA-approved procedures to analyze for the presence of Chlamydia trachomatis (CT) and Gonorrhea (GC) by the IDPH State Laboratory.

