- a. PWUD interviews: 90 study participants will be enrolled (included in total below).
- b. PWUD surveys/biosurveys: A minimum of 100 study participants will be enrolled, though we will continue enrolling to a maximum of 800. The exact number will

depend upon recruitment speed, staff availability, and timing of the consolidation of results for UH3 application (approximately spring of 2019). We will seek to capture interest in future research related to this project from consented PWUD subjects. The consent provides permission to the optional future contact for research. Information provided on the locator form will be used for contact in the future for related research projects.

- c. Stakeholder Interviews: up to 60 stakeholders working in the Delta region will be enrolled, including:
 - Harm reduction organization staff who provide syringe services to PWUD clients
 - Law enforcement officers including community corrections
 - Public officials and court representatives including judges
 - Addiction treatment providers
 - Emergency medicine
 - Pharmacists
 - Local Health Department Administrators

b) Method of subject selection

- a. **PWUD Interviews:** Key informant interviews will be performed for individuals who have used opioids or stimulants by any route, or injected any drugs, to get high in the past 30 days. These key informants will be referred by harm reduction organizations that are partnering organizations in this study (see section 5. Location below).

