- b. **PWUD surveys :** Respondent-Driven Sampling (RDS) will be utilized with the harm reduction organization client population. RDS has been widely applied to study hard to reach populations.[13-17] RDS is an efficient method that uses respondents' network connection to generate a sample that approximates a probability sample allowing for valid statistical analysis. RDS uses a small number of initial seeds (generally highly socially connected clients referred by the harm reduction organization), each of who will receive no more than six vouchers to recruit other people who have injected drugs or used opioids or stimulants to get high within the past 30 days. These seeds will be recruited by the harm reduction partners through their existing client base. All efforts will be made to ensure that seeds are diverse from a standpoint of race/ethnicity, gender, and county of residence. New seeds can be added if chains of referral stop. Respondents receive an incentive payment for their participation and an incentive for each voucher that they distribute that produces an additional eligible respondent. The process is then repeated with each new respondent. This system of incentive payments, which is crucial to RDS, also serves to maintain ongoing contact

with respondents and will aid in our retention of respondents. Potential clients who are referred by the harm reduction partners will meet with study staff who will provide eligibility screening, perform the electronic consent process, complete locator form which will be used if a future amendment for this study includes a follow up surveys and/or interviews, and confirmatory test results (SOC), and administer the survey. If consented to by the study participant, results from routine HIV/HCV screening performed for these clients by the harm reduction organization staff will be communicated to the co-PI ([name]).

- i. In addition to RDS, we will place our study recruitment flyers at spaces available to the public. These spaces will include local health departments, social services organizations, public parks, public transportation, and food pantries. The appropriate permissions will be sought from the venue operators prior to posting the flyers.

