- Assistance with the hiring of study staff who will be located at the community organizations to conduct consenting, interviews and survey administration.
- Assistance with study equipment purchasing, such as iPads, in instances where they have access to lower pricing
- Provide space for consenting, interviewing or survey administration if needed.

[name],

[name] will serve as a consultant on this project. Additionally, he will provide training to study staff, and will participate in the interviewing of study subjects.

Community Action Place, Inc. (CAP)

CAP will be engaged in research. They will recruit from their clients who participate in syringe services as well as HIV/HCV testing services.

[name], Director, Institute for Infectious Disease Research – New York University
[name] will conduct analysis on identified study data.

[name], Postdoctoral Fellow, – New York University
[name] will conduct analysis on identified study data.

[name], MPH, Assistant Professor - Cornell University
[name] will support qualitative analysis development, instrument guide development and analysis and will participate in the interviewing of study subjects.

[name], CHES – Austin Peay State University
[name] will adapt the survey and qualitative instruments and lead in the analysis pertaining to the sexual and gender minority population in ETHIC on de-identified data only. She will lead on conference abstract and manuscript development.

8) Data analysis

Data analysis will be performed by Drs. [name], [name], [name], Friedman, [name] and [name] as well as [name]. Additional statistical analysis will be performed by members of the Biostatistics Laboratory at the University of Chicago.

- a) Descriptive statistics, network characteristics and disease burden analyses:
Demographic, drug use characteristics, sexual risk behaviors, psychosocial measures and HIV, HCV, HBV and STD status will be analyzed using standard descriptive and comparative statistical analyses. Specifically, t-tests and Chi-square analyses will compare groups for continuous and categorical variables; logistic regression will examine factors associated with disease presence; and repeated measures ANOVA assess factors associated with re-infection/treatment failure. Statistical significance will be assumed with p-values <0.05.

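### Protocol section 8(a) plans standard unweighted analysis of infection status in a respondent-driven sample, and nothing applies the protocol's own RDS estimators to prevalence

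*Protocol*

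**What the plan says.** **Target.** Protocol section 3(i) says that participants will be "screened at baseline and follow-up to determine disease prevalence and incidence in the population", and that the results will "characterize the disease burden in the rural PWUD population versus the rest of the IDR and national trends".

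**Recruitment.** Section 4(b) describes RDS. The seeds are "generally highly socially connected clients referred by the harm reduction organization", each participant may pass on up to six vouchers, and the process repeats with each new respondent. The same section adds flyers, public events and online advertisements. Enrolment is open-ended within limits: "A minimum of 100 study participants will be enrolled, though we will continue enrolling to a maximum of 800".

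**Analysis.** Section 8(a), whose title includes disease burden, states that "HIV, HCV, HBV and STD status will be analyzed using standard descriptive and comparative statistical analyses". It continues: "Specifically, t-tests and Chi-square analyses will compare groups for continuous and categorical variables; logistic regression will examine factors associated with disease presence". The threshold is p<0.05. The section mentions no weight, recruitment chain or interval.

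**RDS estimators.** These appear only in section 8(o), on population size. It says that several RDS weighting estimators, including Volz-Heckathorn and Successive Sampling, will be compared for best performance. It gives no criterion for choosing and no interval method, and it does not refer to section 8(a).

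**SAP.** It does not mention RDS, weighting or infection prevalence.

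**The concern.** A voucher sample is not a simple random sample. People with more contacts have more chances of being recruited, and people in one chain tend to resemble each other. Section 8(a) handles neither feature, so an analyst who follows it reports the raw proportion infected.

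Two errors can follow:

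- **Bias.** If better-connected people are infected more or less often than others, the raw proportion misstates prevalence in the population. This error does not shrink as enrolment grows.
- **Precision.** If infection clusters along chains, an ordinary binomial interval overstates how well prevalence is known.

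The protocol makes the first plausible. Its background on social networks reports that in another rural setting "degree centrality (i.e. connected network position) were associated with increased HCV risk". That does not show the link exists in southern Illinois.

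The prevalence is to be set beside regional and national figures, and section 8(e) says survey data will inform service expansion. The documents give no benchmark value or formal test, so they cannot show whether any decision would change.

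**Working it through.** The plan states no precision, interval or power figure for prevalence, so there is none to reproduce. The figures below only illustrate size.

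**Inputs from the documents**
- HCV antibody prevalence p = 0.478 (Protocol, ECHO addendum, Background). No denominator is given, and the figure is not said to be weighted.
- n = 100 and n = 800, the enrolment limits (section 4(a)); n = 173, the number enrolled 8/2017 to 7/2019 (section 9).

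**Assumptions (not in the documents)**
- Design effect D from 1 to 2.
- Ratio r of mean network size, infected to uninfected, from 1 to 2.

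**Step 1: half-width of a 95% interval** = 1.96 × √(D × p(1−p)/n), with p(1−p) = 0.478 × 0.522 = 0.2495.

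| n | D=1 | D=1.5 | D=2 |
|---|---|---|---|
| 100 | 9.8 | 12.0 | 13.8 |
| 173 | 7.4 | 9.1 | 10.5 |
| 800 | 3.5 | 4.2 | 4.9 |

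(percentage points; at n=100 and D=2 the unrounded value is 13.846)

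**Step 2: true coverage of an interval that assumes D=1** = 2Φ(1.96/√D) − 1. This gives 95.0% at D=1, 89.0% at D=1.5 and 83.4% at D=2.

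**Step 3: effect of weighting on the point estimate.** If the chance of recruitment is proportional to network size, the inverse-degree estimate is (p/r) / (p/r + 1 − p).

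| r | Weighted estimate from a crude 47.8% |
|---|---|
| 1 | 47.8% |
| 1.14 | 44.5% |
| 1.25 | 42.3% |
| 1.5 | 37.9% |
| 2 | 31.4% |

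The row r = 1.14 is what results if half the population has twice the network size of the rest and prevalence is 60% against 40% in the two halves: (0.6×2 + 0.4×1)/(0.4×2 + 0.6×1) = 1.6/1.4 = 1.14. The shift is then 3.3 points. If infected people had smaller networks, r would be below 1 and the shift would go the other way.

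**Step 4: would chain-clustered standard errors repair the tests?** Simulation used 4,000 replicates, n=100, D=2 and ten chains of assumed sizes 46, 20, 10, 8, 5, 4, 3, 2, 1 and 1. It compared an ordinary chi-square test with simple clustered errors (CR1, t with 9 degrees of freedom), both at nominal 5%. The ranges are over repeat runs.

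| Factor | Chi-square | CR1 clustered |
|---|---|---|
| Varies between individuals | about 5% | 9 to 10% |
| Constant within chains | 11 to 13% | 17 to 20% |

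With few, unequal chains the simple correction is worse than none. For individual-level factors the planned test already holds its level.

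**The case against.** **Section 8(o) may already cover prevalence.** Only its second sentence ties Successive Sampling to population size. Volz-Heckathorn estimates means and proportions, so listing it suggests wider use. This is a fair reading, and it is why the point is a missing link and not a contradiction. A reader might infer that the protocol ignores RDS weighting altogether, and section 8(o) shows otherwise. Even so, nothing applies the weighting to section 8(a), and an analyst could follow 8(a) literally.

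**Section 8(a) plans no intervals.** True. The coverage figures describe an interval that an analyst would have to add. They matter because a prevalence set against regional and national figures would normally carry one.

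**Recruits from flyers, events and online advertisements are partly covered.** Section 6 gives vouchers to survey participants without distinguishing route of entry, and section 4(b) allows new seeds. Such a recruit therefore already acts as a seed. What is missing is a record of the source and a rule for analysis.

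**The tests are sound for individual factors.** This stands. A reader might infer that the t-tests, chi-square tests and logistic models are invalid in general. The documents do not support that: section 3(i) speaks of individual factors, and these are little affected. Inflation would need a factor that follows the chains. County is a candidate, since "All efforts will be made to ensure that seeds are diverse from a standpoint of race/ethnicity, gender, and county of residence", but diverse seeds do not prove that chains stay within a county, and section 8(a) names no county comparison.

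**The sizes are assumed.** They are, and every range includes no effect. Degree centrality in a mapped network elsewhere is also not the same as the self-reported network size that RDS weights use.

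**Conclusion.** The concern holds for prevalence. The protocol aims at prevalence in a population, recruits mainly by chains, names estimators suited to that design, and then specifies standard unweighted analysis without connecting the two.

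The omission is certain; its numerical effect is unknown. At an assumed design effect of 2, a naive 95% interval covers about 83%, and the half-width at 47.8% and n=100 is 13.8 points rather than 9.8. At assumed network-size ratios of 1 to 2, weighting moves a crude 47.8% by 0 to 16.4 points (47.8 − 31.4). With a design effect of 1 and no relation between network size and infection, nothing changes. The documents therefore do not show that the reported prevalence is wrong, only that the plan does not guard against it.

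The point does not extend to the SAP, whose outcomes do not include infection prevalence.

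**What to change.** In Protocol section 8(a):

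1. Estimate baseline prevalence with one RDS estimator named in advance from section 8(o), for example Volz-Heckathorn with Successive Sampling as a sensitivity analysis. Give an RDS bootstrap interval and report the unweighted estimate alongside.
2. Record each participant's recruitment source. Treat flyer, event and online recruits as seeds, and run a sensitivity analysis that excludes them.
3. Confirm that the survey records each respondent's personal network size. Section 3(h) refers only to egocentric network data, and the weights cannot be computed without it.
4. Leave the group comparisons and logistic models for individual-level factors as planned. For factors that may follow recruitment chains, such as county, report the number and sizes of chains and treat p-values as exploratory. Do not prescribe simple CR1 chain-clustered errors.

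No SAP change is needed.

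**Cost.** A few sentences in section 8(a), a cross-reference to section 8(o), and modest extra analysis. Referral codes for tracing chains already exist (section 5, Community Action Place). Reported intervals will be wider. If network size was not collected, weighted estimates are not possible, and that should be stated as a limitation.

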- f) **Stakeholder Interviews:** Stakeholders including harm reduction organization staff members, law enforcement including communication corrections officers, clinical providers, and local public health administration will be interviewed to explore the community level barriers to care facing PWUD in accessing care (Appendix 3) Stakeholders who have membership in the Southern Illinois Opioid Taskforce or who have been referred by members of the Taskforce or local health departments will be invited by email to take part in the study interviews. Flyers will be handed out by the staff at the Center for Rural Health and Social Services Development (CRHSSD) at the Southern Illinois University School of Medicine as well as posted at local health departments. Interviews will be performed by trained study staff. Interviews will last approximately 60 minutes. Interviews will be audio-taped and transcribed verbatim.
- g) **Stakeholder Demographic Survey:** Following the interviews, stakeholders will be asked to complete a brief demographic survey. The information captured through this survey will be used to help us contextualize the background and general traits of these participants.
- h) **PWUD Survey:** We will use Respondent Driven Sampling (RDS) to recruit PWUD and people who use opioids through harm reduction organizations operating in the Delta region to perform a survey analysis to understand risk behaviors, health services preferences, social network estimates and estimates of population size and demographics. Further discussion of RDS methods and sample size are discussed in the section 4b "Method of participation selection" below. In distinction from the interviews, we will include participants who inject any psychoactive drug including non-opioids given the high proportion of methamphetamine users in the region, as well as individuals who use opioids or stimulants to get high through intranasal, smoke, or ingestion route. A survey instrument will be used to gather information related to the following domains: demographics, drug use behavior, overdose experience, sexual risk behavior, HIV/HCV/STI testing history, health care utilization and preferences, barriers to care, and egocentric network data. The survey instrument is adapted from the Social

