- Oral swabs to test for CT/GC using a combination of FDA-approved and internally-validated procedures as performed by the IDPH State laboratory

Rapid assay preliminary results will be reported directly to the participant during the visit according to standard procedure. In the event that the HIV and/or HCV finger stick or oral swab screen is positive, phlebotomy for serum samples for HIV RNA

(confirmatory to rapid assay), and blood for HCV RNA (confirmatory to rapid assay) will be obtained. Additional serum will be sent to the NIH/NIDA-funded GHOST laboratory to perform HCV sequencing (see Section i below) sometime after collection (weeks/months; non-diagnostic) Samples sent to the GHOST lab will be de-identified. Biospecimen analysis results will be reported to a study PI ([name]), the Harm Reduction partner from whom the participant was recruited, and the proper local health department (according to standard IDPH procedure). The HR partner will be responsible for contacting all participants with their screening results. Study personnel will facilitate linkage to care, providing the introduction of the participant to the local health department staff. Additionally, we will provide the participant with transportation, if required, and will confirm that they attended their first confirmatory testing appointment. Positive results for any disease will also be reported to the appropriate local health department for follow up by a DIS and provision/referral to appropriate services according to standard procedures.

- For CT/GC - The LHD will follow up first with the provider. If they have not treated, then they contact the patient if they are age 18 or older and can treat since they have the lab result. Those under age 18 can only be contacted by the original HR partner.
- For HCV - For participants who test positive for HCV, we will assist them with attending their first confirmatory testing appointment, which will be with their primary care physician or a local infectious disease specialist.
- For HIV - Treatment and follow up is arranged through Southern Illinois Care Connect for services through the Ryan White Program which is operated by the Jackson County Health Department HIV Care Connect Grant.

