egocentric networks (both nonsexual social and sexual) and RDS connections. Network structure will be estimated by evaluating main component size, the nodes located in the largest connected component of the network, and average component size. Measures will include the average geodesic distance between participants, network centralization (degree the network centralizes around one or a small group of participants), ranked kplex measure of cohesion, and transitivity (degree which triadic closure occurs)[21-26] Individual and network factors associated with infectious diseases will be determined.

- o) PWUD Population Size Estimation: Multiple estimators for RDS weighting for network factors will be tested for best performance, including the Volz-Heckathorn and the Successive Sampling Estimators.^[27, 28] For the Successive Sampling Estimator, we will use mixed-methods triangulation to estimate PWUD population size in the delta regional authority, including survey data, fatalities related to overdose, and drug arrest data.^[29]
- p) HCV sequencing analysis: analyses of minimum distances, maximum distances, nucleotide diversity, frequency of major haplotypes and calculations for sequence relatedness will be performed on the HVR1 quasispecies using statistical and bioinformatics toolboxes implemented in MATLAB software package version 2011B (The MathWorks, Inc., Natick, MA). The minimum distance between intra-host HCV variants will be calculated, and a minimal hamming distance for the relatedness threshold (3.7%) will be used to identify epidemiologically confirmed outbreaks, as has been previously described.^[30] Previous work by key investigators have used this approach in collaboration with the CDC to study HCV outbreaks.^[31, 32] Further analytic approaches will be considered in close collaboration with the GHOST laboratory.
- q) **Evaluation of Harm Reduction Services Referrals. Evaluation will be performed using the RE-AIM framework (Reach, Evaluation, Adoption, Implementation and Maintenance) using survey, interview and CAP program data.**
 - 1.) Reach Analysis: Descriptive analyses will be conducted initially to examine variable distributions and identify outliers, and data will be summarized using frequencies and measures of central tendency. The absolute number and proportion of participants accepting referral to the harm reduction intervention will be calculated at each assessment point (Reach: absolute (%) outcome).

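### Protocol 8a assigns repeated measures ANOVA to re-infection/treatment failure, which neither document defines; on the natural yes/no reading the method does not fit

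*Protocol*

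**What the plan says.** Protocol 8) a) lists HIV, HCV, HBV and STD status together and then allots methods: t-tests and chi-square tests for group comparisons, "logistic regression will examine factors associated with disease presence", and "repeated measures ANOVA assess factors associated with re-infection/treatment failure". Significance is p<0.05. This is the only mention of re-infection, treatment failure or repeated measures ANOVA in either document.

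Protocol 3) i) schedules screening at baseline and then "every 6 months until the beginning of the drawn down period of the study", with no fixed number of visits. In a COVID-19 shutdown, "specimen collection will be deferred until in-person data collection is possible". After a positive rapid screen, "blood for HCV RNA (confirmatory to rapid assay) will be obtained"; no rule turns serial results into re-infection or failure.

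The SAP does not mention this analysis. Its HCV effectiveness outcome (2, vi) is access to care after a reactive test. Its longitudinal comparison is baseline against 6 months in newly engaged participants, with no model named.

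**The concern.** Re-infection can occur only after an earlier infection has ended, and treatment failure only after treatment. They are different events in different people, joined here by a slash. If each is recorded as yes or no, repeated measures ANOVA treats a 0/1 result as a continuous response with constant variance on a common set of visits. None of these conditions holds when risk differs by group, visits vary in number and some are deferred.

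Two things are at stake. The precision reported for a risk factor can be wrong in either direction, depending on which group is smaller. And because disease, outcome, population and scale are all open, each could be settled after the data are seen while the protocol still promises a test at p<0.05.

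**Working it through.** The plan gives no event rate, power or effect size for this analysis, so there is no figure of its own to reproduce. What follows is illustration, and every risk in it is an assumption.

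**1. Why the variance fails.** A yes/no result with risk p has variance p(1-p): 0.0475 at 5%, 0.09 at 10%, 0.16 at 20%. If a factor matters, its groups have unequal variances.

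**2. Worked case.** Take 100 at-risk people, four follow-ups and interval risks of 15% and 5%. The variance of a person's mean is 0.15×0.85/4 = 0.031875 in the higher-risk group and 0.05×0.95/4 = 0.011875 in the other. The ANOVA pools these.

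- 20 at higher risk, 80 at lower. True SE = √(0.031875/20 + 0.011875/80) = 0.0417. Pooled variance = (19×0.031875 + 79×0.011875)/98 = 0.01575, so the ANOVA SE = √(0.01575×(1/20+1/80)) = 0.0314. Ratio 0.75: too narrow.
- 80 at higher risk, 20 at lower. True SE = √(0.031875/80 + 0.011875/20) = 0.0315. Pooled variance = (79×0.031875 + 19×0.011875)/98 = 0.0280, ANOVA SE = 0.0418. Ratio 1.33: too wide.
- 50 and 50. Both are 0.0296. Ratio 1.

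**3. Coverage by simulation.** There were 20,000 studies per setting, with 40, 83 or 100 at-risk people, 2, 4 or 6 follow-ups, and interval risks of 5 vs 10%, 5 vs 15% or 10 vs 20%, independent between intervals. Six follow-ups is the most that the 36 months in Protocol 10) allows.

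| Share in higher-risk group | Coverage of nominal 95% interval |
|---|---|
| 20% | 84-91% |
| 35% | 89-93% |
| 50% | 94-95% |
| 65% | 96-98% |
| 80% | 98-99% |

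With equal groups but fewer people, coverage is about 79-95% at 10 people and 90-95% at 17, by setting.

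A person-interval logistic interval (log odds ratio, a different scale) covers about 95-96% with 83-100 people and 4-6 follow-ups. In sparser settings among the 40-100 it is conservative, up to 99.5%. At 17 people with 80% at higher risk it falls to about 93%.

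**4. Tests when risks are equal.** With 40-100 people and four follow-ups, the between-group ANOVA test rejects in 4-5%. The group-by-time test was checked separately (4,000 studies per setting, 40 or 400 people, 5% risk per visit, outcome staying positive once it occurs, no sphericity correction). It rejects in 6.4-7.1%.

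**5. Visits.** If the ANOVA were run on complete cases (the protocol does not say), the share with all visits is (1-m)^V for an assumed independent miss rate m. Over four follow-ups, 10/20/30% missed leaves 66/41/24%.

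**6. Scale, HCV only.** Protocol 4) a) states: "A minimum of 100 study participants will be enrolled, though we will continue enrolling to a maximum of 800". Protocol 9) mentions 173 enrolled by July 2019. The ECHO addendum's Background gives 47.8% antibody-positive and 10.4% with treatment access, without the denominator of the latter. Expected treated for 100/173/800 enrolled:

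- 10.4% of antibody-positives: n×0.478×0.104 = 5.0/8.6/39.8.
- 10.4% of everyone: n×0.104 = 10.4/18.0/83.2.

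At an assumed 5-20% failing, that is 0.2-2, 0.4-4 and 2-17 failures. For scale, 1 of 9 has an exact 95% interval of 0.3-48%, and 8 of 83 has 4-18%. These counts say nothing about gonorrhoea, chlamydia, HIV or HBV.

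**The case against.** The strongest reply is that the line may not concern a yes/no outcome. Serial quantitative RNA, or repeated continuous factors compared between outcome groups, would make the method usable. That stands as a possibility, but the protocol states neither and does not say whether RNA is quantitative. The continuous measures it does name, "analyses of minimum distances, maximum distances, nucleotide diversity, frequency of major haplotypes", belong to the relatedness analysis in 8) p).

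Second, the protocol promises a test and not an interval, and the between-group test is close to nominal. This is a fair limit on the coverage figures. A reader might infer from them a general excess of false positives, which the between-group results do not support. Nor is every ANOVA test safe, as the group-by-time result shows.

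Third, this is one clause under a largely descriptive heading in a study that says it is not a clinical trial (Protocol 19), and the SAP does not carry it. That stands, and it limits the priority.

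Fourth, a reader might infer that events will be too few for any model. That rests on HCV figures alone, recorded before the ECHO effort to widen treatment. Protocol 8) a) lists other infections, and gonorrhoea and chlamydia are also screened for and treated.

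Fifth, a reader might infer that treatment data are missing. Treatment is not spelled out among the survey domains in Protocol 3) h), which include "HIV/HCV/STI testing history, health care utilization and preferences, barriers to care, and egocentric network data". But the instrument is an appendix not available here, and the addendum reports treatment access, so something was recorded.

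The missing at-risk set would affect a logistic model equally. It is a gap in definition, not a fault of ANOVA.

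**Conclusion.** The point holds, with limited reach. What is firm is that the outcome, disease and at-risk set are undefined, and that the SAP leaves the line neither adopted nor withdrawn. The mismatch of method is conditional on the yes/no reading, which the parallel use of logistic regression makes the natural one.

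The size depends on assumed risks, independent intervals and group shares. Intervals are clearly too narrow when the higher-risk group is small, too wide when it is large, and about right with equal groups of reasonable size. That last reassurance fails at 10-17 people. No SAP RE-AIM outcome is affected, and Protocol 8) a) does not rank this analysis among the others. It should be corrected, but it does not threaten the study's main results.

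**What to change.** 1. Name the disease. Define re-infection and treatment failure separately, each with the person-intervals at risk.
2. Replace the ANOVA with a binary model for repeated data on those intervals: GEE or mixed logistic regression, or a discrete-time logistic or complementary log-log model that allows for interval length. Where the events actually observed for that disease are few, use a Firth penalty, or report counts with exact intervals. A robust standard error on a linear model is not enough: with equal risks, 40 people split 20:80 and four follow-ups, a Welch test rejects in 7-17%.
3. If a continuous outcome was intended, name it and use a mixed model that accepts unequal visits.
4. If the treatment or RNA data needed are not captured, declare the line descriptive or withdraw it.

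The cost is a short protocol or SAP amendment, standard software and some data derivation. Before a model is promised, check that treatment status and timing are recorded, and that RNA results, drawn only after a positive rapid screen, can show that an infection ended. If they cannot, the change is one sentence.
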